  - 19 For subjects not on MMF during screening, will start receiving MMF therapy at the Baseline Visit and return for local complete blood count assessments at Weeks 1 and 3 after randomization (see Section 7.2.2.3, [Mycophenolate Mofetil \(Background Therapy\)](#)).
  - 20 IV methylprednisolone administered 0.5 g on baseline and Day 2. If IV corticosteroids must be administered during screening then the FMV urine specimens will be collected prior to the infusion (see Section 7.2.2.2, [Corticosteroids](#)).
  - 21 See Section 7.2.2.2, [Corticosteroids](#).

Notes: Subjects who discontinue therapy will attend their regularly scheduled study visits to the end of the study. Subjects who withdraw consent and terminate the study early or discontinue treatment early should be advised to attend both Visit 15 and the Safety Follow up Visit (Visit 16).

Abbreviations: AE=adverse event; BP=blood pressure; CBC=complete blood count; ECG=electrocardiogram; FMV=first morning void; HRQoL=health-related quality of life; IV=intravenous; LN=lupus nephritis; MMF=mycophenolate mofetil; QTcF=QT interval duration corrected for heart rate using method of Fridericia; SAE=serious adverse event; SELENA-SLEDAI=Safety of Estrogens in Lupus Erythematosus National Assessment - Systemic Lupus Erythematosus Disease Activity Index; SLE=systemic lupus erythematosus.

---

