### 2.1 Dose Rationale

This Phase 3 study is designed to evaluate the treatment benefit of Orelvo 23.7 mg BID versus placebo. Orelvo and/or placebo are herein referred to as study treatment. The selection of Orelvo dose in this study (see Section 7, [Study Treatments](#)) was based on the previous experience with this drug in the Phase 2 study (AURA-LV). In AURA-LV, subjects were administered voclosporin 23.7 mg BID, 39.5 mg BID, or matching placebo. Low-dose voclosporin was significantly superior to placebo in the proportion of subjects achieving complete renal response at Week 24 ( $p=0.045$ ). There was no increase in efficacy with the higher dose and no significant differences between the 2 voclosporin groups in achievement of renal response.

Orelvo 23.7 mg BID will be administered as a fixed dose without the use of therapeutic drug monitoring. Population PK analyses of voclosporin concentrations from the clinical development program (including healthy subjects, subjects with renal impairment, subjects with hepatic impairment, renal transplant, and plaque psoriasis) demonstrated that weight did not have a significant effect on the PKs of voclosporin. The protocol contains provisions for

management of dose based on safety concerns, in particular, BP and renal function. The safety data from the use of voclosporin demonstrates that these risks are dose-related, reversible, and can be managed by dose reduction and temporary interruption.

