### **5.2 Inclusion Criteria**

The following inclusion criteria must be met for each subject:

1. Written informed consent before any study-specific procedures are performed.
2. Male or female subjects with a minimum age of 18 (or legal age of consent if >18 years) to 75 years of age, inclusive, at the time of screening (Visit 1).
3. Previous diagnosis of SLE according to the American College of Rheumatology criteria (1997; see [Appendix 5](#)).
4. Subjects with evidence of active nephritis, defined as follows:

Kidney biopsy result within 2 years prior to screening indicating Class III, IV-S, IV-G (alone or in combination with Class V), or Class V LN (see [Appendix 3](#)) with a doubling or greater increase of UPCR within the last 6 months to a minimum of  $\geq 1.5$  mg/mg for Class III/IV or to a minimum of  $\geq 2$  mg/mg for Class V at screening. Biopsy results over 6 months prior to screening must be reviewed with a medical monitor to confirm eligibility.

OR

Kidney biopsy result within 6 months prior to screening indicating Class III, IV-S, or IV-G (alone or in combination with Class V) LN with a UPCR of  $\geq 1.5$  mg/mg at screening.

OR

Kidney biopsy result within 6 months prior to screening indicating Class V LN and a UPCR of  $\geq 2$  mg/mg at screening.

A biopsy can be performed during screening, if not available. The above criteria must be fulfilled at baseline.

5. In the opinion of the Investigator, subject requires high-dose corticosteroids and immunosuppressive therapy.
6. Subject is willing to take oral MMF for the duration of the study, either by continuing current MMF therapy or by initiating it on or before the Baseline Visit.
7. Women of childbearing potential must have a negative serum pregnancy test at screening and a negative urine pregnancy test at baseline. Two effective forms of contraception must be used simultaneously unless abstinence is the chosen method. Subjects must use effective contraception during the study (see Section 5.4, [Adequate/Effective Contraception](#)).

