## **5.5 Withdrawal of Subjects**

Subjects may voluntarily withdraw from study participation at any time for any reason. Alternatively, subjects may be withdrawn at the Investigator's discretion if it is in the subject's best interest.

Every effort should be made for subjects who withdraw from the study, either voluntarily or at the Investigator's discretion, to undergo end of study assessments (Visit 15), if possible. If possible, the subject should also be advised to come for the Safety Follow-up Visit 4 weeks after last dose. If a subject refuses end of study procedures, the reason for refusal should be fully documented in the subject's source document and recorded in the study specific electronic case report form (eCRF). It is the subject's right to withdraw from the study without providing a reason. In this case, the source documents and the eCRF should document the reason for discontinuation as "withdrawal of consent." Withdrawn subjects will not be replaced.

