## **5.6 Discontinuation of Study Treatment**

If any subject is discontinued from study treatment, the reason for discontinuation will be documented in the eCRF. If the reason for discontinuing study treatment is an AE or an abnormal laboratory test result, the specific event or test will be recorded in the eCRF. Except for cases involving pregnancy, subjects who are discontinued from study treatment should undergo all study assessments up to and including (Week 52 or Early Termination Visit – Visit 15), if possible. The subject should also be advised to come for the Safety Follow-up Visit 4 weeks after last dose. Guidance on when study treatment must be discontinued is in Section 7.6, [Orelvo/Placebo Dose Modification](#).

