### 7.2.2.3 Mycophenolate Mofetil (Background Therapy)

Subjects receiving MMF prior to randomization will continue without interruption.

- Subjects must be counselled on the risk of pregnancy while taking MMF and the need for adequate contraceptive precautions (see Section 5.4, [Adequate/Effective Contraception](#)).
- Subjects on AZA or mycophenolate sodium at screening must switch to MMF at baseline (Day 1).
- For subjects who are not already taking prescribed MMF prior to randomization, the dosing of MMF will start at 500 mg BID for a total daily dose of 1 g/day for the first week, increasing to 1 g BID for a total daily dose of 2 g/day for the second and subsequent weeks (i.e., beginning on Day 8).
- Complete blood count must be performed locally at Weeks 1 and 3 in subjects not already taking MMF at screening (unscheduled visit or not).

All subjects will take MMF BID (morning and evening), before meals (i.e., on an empty stomach), with a glass of water. If a dose is missed, the subject should take the next correct dose rather than “doubling up” at the next dosing time point. A stable dose of MMF will be maintained throughout the study. Dose changes or interruptions are permitted for clearly documented safety reasons only.

- Approval by the Medical Monitor is required for subjects taking a dose other than 2 g/day MMF from randomization onwards (e.g., total daily dose of 1 or 3 g/day).
- If GI disturbance or other side-effects occur with MMF, the 1 g BID dosing may be changed to 500 mg four times daily.
- If a subject has an ANC  $<1,500/\text{mm}^3$  at any study visit, the dose of MMF should be decreased or interrupted. If a subject has an ANC  $<1,000/\text{mm}^3$  at any visit, the dose should be discontinued and only recommenced when the ANC reaches  $1,500/\text{mm}^3$ . If the subject has a dose interruption of MMF of  $>14$  days, then permanent discontinuation of MMF, therefore the study, should be considered after discussion with the Medical Monitor.
- If deemed necessary by the Investigator on account of leukopenia or other adverse effect, or if the subject weighs 50 kg or less, the dose of MMF may be decreased to a minimum of 500 mg BID.

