### 3 ENDPOINTS

#### 3.1 Primary Endpoint

Renal response at Week 52 will be adjudicated by the Clinical Endpoints Committee (CEC) based on the following parameters:

- UPCR of  $\leq 0.5$  mg/mg, and
- eGFR  $\geq 60$  mL/min/1.73 m^2 or no confirmed decrease from baseline in eGFR of  $>20\%$ , and
- Received no rescue medication for LN (see Protocol Section 7.8, Prohibited Therapy and Concomitant Treatment), and
- Did not receive more than 10 mg prednisone for  $\geq 3$  consecutive days or for  $\geq 7$  days in total during Weeks 44 through 52, just prior to the renal response assessment

The CEC will also take into account the following:

- Subjects who withdraw from the study prior to the Week 52 assessment and provide insufficient week 52 data to determine response will be defined as non-responders. Subjects who discontinue study drug but continue to attend study visits (as is the expectation) will have their data assessed for response.
- eGFR values eliminating a subject from complete remission should be accompanied by a treatment or disease-related treatment-emergent adverse event (TEAE) that impacts eGFR. Full details are given in Section [6.11.1](#).
- The CEC is independent and blinded from the treatment groups.

The primary endpoint estimand is the proportion of subjects showing renal response as adjudicated by the CEC in the ITT population when comparing voclosporin and placebo at Week 52. It is assessed in all randomized subjects who were recruited according to the inclusion/exclusion criteria of the protocol.

The variable is binary and indicates a response if a subject shows, at 1 year, adequate UPCR with no signs of detrimental impact on eGFR. Subjects who cannot be shown to be responders through their 1 year data (or absence thereof) are defined as non-responders.

Intercurrent events include:

- Treatment discontinuation for any reason
  - the subject remains on study, allowing the primary endpoint to be assessed at 1 year.
- Study discontinuation
  - resulting in insufficient information at 1 year to ascertain response status leading to assumed non-response.
- Rescue medication taken at any time prior to the primary assessment at 1 year
  - results in non-response. Rescue medication is adjudicated by the Clinical Endpoints Committee.
- Death at any time prior to the 1 year primary assessment
  - results in assumed non-response.

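### The neutropenia bullet of Protocol 7.2.2.3 prompts study exit when MMF is stopped, against the plan's aim of following subjects who stop treatment to Week 52

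*Protocol*

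**What the plan says.** The clause is in the bullet of Protocol 7.2.2.3 on low absolute neutrophil count (ANC). Once MMF has been interrupted for more than 14 days, "then permanent discontinuation of MMF, therefore the study, should be considered after discussion with the Medical Monitor".

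Other parts of the plan bear on what happens next:

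- **Schedule of Events, notes:** "Subjects who discontinue therapy will attend their regularly scheduled study visits to the end of the study".
- **Protocol 5.6:** apart from pregnancy, "subjects who are discontinued from study treatment should undergo all study assessments up to and including" Week 52 or the early termination visit, if possible. The synopsis has a similar rule, with withdrawal of consent as its exception.
- **Protocol 2.1:** "Orelvo and/or placebo are herein referred to as study treatment".
- **Protocol 5.5:** "subjects may be withdrawn at the Investigator's discretion if it is in the subject's best interest".
- **Protocol 5.2, criterion 6:** "Subject is willing to take oral MMF for the duration of the study".
- **SAP 3.1, treatment discontinuation for any reason:** "the subject remains on study, allowing the primary endpoint to be assessed at 1 year".
- **SAP 3.1, study discontinuation:** "resulting in insufficient information at 1 year to ascertain response status leading to assumed non-response".

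**The concern.** The word linking the MMF stop to the study makes exit a consequence of stopping a background drug, and the protocol gives no reason for that link. None of the four components of renal response in SAP 3.1 requires the subject to be on MMF, so response at Week 52 can still be assessed after MMF is stopped.

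The clause can be reached under the protocol's own thresholds. Exclusion criterion 8 uses an ANC below 1,300/mm³, and only for marrow insufficiency unrelated to active SLE. MMF is to be reduced or interrupted below 1,500/mm³. A subject can therefore enter already under the action level.

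What is at stake is a Week 52 outcome that could have been observed but is scored as non-response, together with the UPCR, eGFR and safety data between exit and Week 52. The tipping point analysis in SAP 6.11.2.4 tests how sensitive the result is to missing outcomes. It does not recover them.

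**Working it through.** **1. The texts side by side**

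| Event | Text | Stays in follow-up? |
|---|---|---|
| Stops therapy | Schedule of Events notes | Yes, to the end of the study |
| Stops study treatment | Synopsis; Protocol 5.6 | Yes; to Week 52 or the early termination visit, if possible, in 5.6 |
| Confirmed QTc increase, study treatment stopped | Protocol 9.1.4.1 | Yes, all remaining visits |
| Study treatment held for blood pressure | Protocol 7.9 | Yes, all visits |
| Treatment discontinuation, any reason | SAP 3.1 | Yes, assessed at 1 year |
| MMF stopped after a gap of more than 14 days | Protocol 7.2.2.3 | Exit to be considered |

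The last row is the only text specific to a permanent MMF stop, and the only row that points towards exit.

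**2. Do the general rules cover a stop of MMF alone?** Not clearly. By the definition in Protocol 2.1, study treatment means Orelvo/placebo, so the synopsis and 5.6 would not apply. Usage varies, however. Protocol 9.2.2 counts background therapy within the study treatment that is dispensed, and SAP 6.9 lists MMF among the study drugs whose exposure is summarized, whereas SAP 6.10 equates study drug with VCS/placebo. The Schedule of Events note speaks of therapy, which can include MMF.

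**3. The plan's own sample size.** Inputs from Protocol 13.2: 20.0% versus 34.4%, two-sided 0.05, 80% power, continuity-corrected chi-square, 162 per arm.

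- d = 0.344 − 0.200 = 0.144; mean rate 0.272.
- Uncorrected n = [1.960·√(2·0.272·0.728) + 0.842·√(0.200·0.800 + 0.344·0.656)]² / 0.144² = 148.7.
- Corrected n = (148.7/4)·[1 + √(1 + 4/(148.7·0.144))]² = 162.3.

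This rounds up to 163 against 162 stated. Power at 162 per arm is 79.9%. The figure reproduces, and nothing here changes it.

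**4. Size per subject**

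- One would-be responder scored as a non-responder: 1/162 = 0.617 percentage points in that arm.
- Relative to the planned difference: 0.617/14.4 = 4.3%.
- The effect is 0 if the subject would not have responded anyway, would have been scored a non-responder for rescue medication, or leaves late enough to supply Week 52 data.

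**5. Which exits can still supply Week 52 data?** Assume nominal visit days (7 × week).

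- SAP 6.2.3 maps early termination data to the closest visit. The midpoint of Week 48 (Day 336) and Week 52 (Day 364) is Day 350, or Week 50.
- Visit 16, 4 weeks after last dose, collects first morning void urine and eGFR (Protocol 9.2.4). SAP 6.2.11 maps all visits to the closest scheduled one. If Visit 16 is attended and that rule applies to it, a last dose from about Week 50 − 4 = Week 46 may also supply Week 52 data.

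So only a late exit avoids assumed non-response. The documents do not fix the exact cut-off.

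**6. Illustration with assumed exit rates.** The documents give none. Suppose a share of each arm leaves under the clause, would otherwise have responded at the planned rate, and is scored as non-response.

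| Share leaving, Orelvo / placebo | Power |
|---|---|
| 0% / 0% | 79.9% |
| 1% / 1% | 79.3% |
| 2% / 2% | 78.7% |
| 5% / 5% | 76.9% |
| 5% / 0% | 69.5% |
| 0% / 5% | 85.6% |

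The last two rows show that the direction depends on which arm loses subjects. The planned rates may already allow for such exits, in which case the change is smaller.

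**7. Other data lost.** Take a hypothetical exit with last dose at Week 4. Ten scheduled visits are missed (Weeks 8, 12, 16, 20, 24, 30, 36, 42, 48, 52). Visit 15 and Visit 16 (about Week 8) replace them, and SAE reporting runs to about Week 4 + 30/7 = 8.3. If Orelvo/placebo also stopped at Week 4, events starting more than 30 days later fall outside the TEAE definition in SAP 6.13.1 in any case.

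**The case against.** The best defence is that the clause mandates nothing. It asks for exit to be considered, case by case, with the Medical Monitor, and Protocol 5.5 already allows withdrawal in the subject's best interest. Because willingness to take MMF throughout is an entry condition, the phrase may simply be shorthand for stopping Orelvo/placebo as well. Protocol 5.6.1 uses similar shorthand: under a heading about study treatment it speaks of continuing in the study. On that reading 5.6 applies and the subject is followed to Week 52. The Schedule of Events note may also be read as already covering MMF.

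Much of this stands. A reader might infer a flat contradiction with the estimand. The documents do not support that, because the clause is discretionary and SAP 3.1 provides for study discontinuation. A reader might also infer that the follow-up rules cover Orelvo/placebo only. The Protocol 2.1 definition points that way, but usage is not uniform.

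The harm is also bounded. Other immunosuppressants are prohibited after randomization (Protocol 7.8.1), and the CEC may adjudicate any treatment as rescue (SAP 6.11.1). If a subject needs a replacement that is so judged, staying in the study would not change the primary result.

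What remains is the wording itself. It names the study, not study treatment, and sites act on the words. Section 5.5 rests on the subject's best interest. The ANC bullet adds a different prompt, a gap in MMF dosing.

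**Conclusion.** The concern holds as a minor wording problem with a cheap remedy. Read as written, the clause prompts study exit after a background drug is stopped, which conflicts in spirit with the plan's retention of subjects who stop treatment. It can turn an assessable Week 52 outcome into an assumed non-response.

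The size is 0 to 0.62 percentage points in one arm per affected subject. The total effect is probably small, but that is a judgement: the documents do not say how often MMF is interrupted for more than 14 days or how often exit would follow.

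A reader might go further and infer that the primary comparison is biased towards one arm or that the trial is underpowered. The documents support neither. The direction of any bias is unknown, the power figures above rest on assumed exit rates, and the plan deliberately counts withdrawals as non-responders.

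**What to change.** Reword the end of the ANC bullet in Protocol 7.2.2.3 along these lines: *then the Investigator should discuss with the Medical Monitor whether MMF should be stopped permanently and whether study treatment should also be stopped. Subjects whose MMF is permanently stopped should continue all scheduled visits and assessments to Week 52 unless they withdraw consent.*

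Leave Protocol 5.5 unchanged, so that withdrawal in the subject's best interest remains possible. The protocol text need not cite the SAP.

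The cost is a minor wording amendment, plus visits that are already scheduled for the subjects concerned: up to 10 each if exit would have come at Week 4. There are no new procedures and no change to the SAP, the sample size or the significance level.

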### 7.3 Package and Labeling

All study treatments provided by Aurinia will be packaged and labeled for Aurinia by appropriately qualified vendors according to all applicable local and country regulatory

requirements. All packaging and labeling operations will be performed according to GMP and Good Clinical Practice (GCP).

Study-treatment wallets provided to sites and to subjects will be labeled in the appropriate local language, according to local regulatory requirements.

Wallet label information will be appropriately documented in the Drug Accountability Form after the container has been dispensed to the subject.

## **7.4 Study Treatment Allocation**

For purposes of randomization, each eligible subject will be assigned to 1 of the 2 treatment groups in a 1:1 ratio using IWRS. The randomization will be central-based and stratified by biopsy class (Class V only versus Others) and by prior MMF use at time of the Screening Visit. Randomization will additionally be blocked by region.

## **7.5 Site Supply, Storage, Accountability**

### **7.5.1 Site Supply**

Once a site has been approved for study initiation, the site will be supplied with an initial stock of study treatment. The need for study treatment resupply will be assessed on a regular basis taking into account the number of subjects enrolled at the site.

### **7.5.2 Storage**

Orelvo softgel capsules and matching placebo capsules will be supplied in cartons containing 168 capsules in 4 wallets of 42 capsules each.

The Investigator must ensure the availability of proper storage conditions. All study treatment supplies provided for this study will be stored in a secure area with restricted access at the study site. The capsules must be stored at a controlled room temperature between 15 and 30°C (59-86°F). The Investigator must document and inform the Site Monitor about temperature deviations outside the acceptable range. Subjects will be instructed to store the study treatment at room temperature between 15 and 30°C (59-86°F).

Each site should have a thermometer that records minimum and maximum temperatures daily. Maintenance of a temperature log is mandatory. The log should be updated by site personnel during normal working hours. This log must be available for review by the Site Monitor during on-site monitoring visits.

### **7.5.3 Accountability**

The Investigator at each site is responsible for study treatment supplies. The Investigator will ensure that adequate records of the receipt, dispensing, and return of the study treatment are

kept and that the study treatment is used only for subjects enrolled in the study. All data regarding the study treatment must be recorded on the relevant forms provided.

Each study site will maintain a drug inventory/dispensing record for all drugs dispensed and returned. At the end of the study, 1 copy of the drug inventory/dispensing record should be sent to Aurinia for the central study file. The original will be kept in the site files.

After completion of the study, or if it is prematurely terminated, all unused materials will be returned to Aurinia. The decision to destroy study treatment at a site must be made by Aurinia. If the study treatment is destroyed at a site, the Investigator must receive Aurinia approval of the process and forward the certificate of destruction to Aurinia.

Records of IV methylprednisolone, oral corticosteroids, and MMF must be maintained (prescribed dose, dose adjustments and reasons) in the source notes and must be transcribed into the eCRF.

